- Screening
- After Cycle 2: On C2D25 ( $\pm 1$  day). This corresponds to 10 days ( $\pm 1$  day) after the 4th dose (after C2D15) of study drug administration

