#### **3.2 Secondary Endpoints**

The key secondary endpoint is

- OS

Other secondary endpoints are:

- Rate of CR as best overall response achieved at the end of randomized regimen (A+AVD or ABVD) per IRF assessment using the Revised Response Criteria for Malignant Lymphoma
- AEs, SAEs, assessments of clinical laboratory values, and vital sign measurements
- EFS
- DFS
- ORR
- DOR per IRF
- DOCR per IRF
- The rate of patients not in CR that received irradiation
- CR rate per IRF at the end of frontline therapy
- The rate of Cycle 2 PET negativity
- PRO per European Organization for Research and Treatment of Cancer (EORTC) QLQ-C30

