#### **Other Secondary Efficacy Endpoints**

CR per IRF will be analyzed based on the ITT population. CR rate per IRF is defined as the proportion of patients who achieve CR at the end of treatment with randomized regimen (A+AVD or ABVD) as determined by an IRF. CR rates between the 2 treatment arms will be compared using a stratified Cochran-Mantel-Haenszel (CMH) test. A logistic regression model will be used to estimate the treatment effect in terms of odds ratio. The odds ratio and its associated 95% CIs will be presented. Sensitivity analyses for CR per IRF will be performed using the response-evaluable population. CR rate per investigator will also be analyzed similarly using the ITT population.

Comparison of the ORR between the 2 treatment groups will be conducted using the stratified Cochran-Mantel-Haenszel test. The 95% CI of the difference of the response rates

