5.4 Data Handling

5.4.1 Methods for Handling Missing Data

All available efficacy and safety data will be included in data listings and tabulations. Data that are potentially spurious or erroneous will be examined under the auspices of standard data management operating procedures.

In general, missing data will be treated as missing and no data imputation will be applied, unless otherwise specified. For Quality of Life Data, missing elements may be substituted with the average of non-missing items per published methods of analysis.

Last observation carried forward method and multiple imputation method may be considered for some clinical outcomes as deemed appropriate.

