5.8.2 Primary Efficacy Analysis

Final analysis of mPFS will be performed when 260 mPFS events have been observed, which is estimated to occur by 24 months after the last patient is randomized.

Stratified log-rank testing will be used to compare mPFS between the 2 treatment arms as the primary analysis. The stratification factors include region and number of IPFP risk factors at baseline (Section 5.2). The hazard ratios along with the 95% confidence interval (CI; 2-sided) will be estimated using the stratified Cox model with treatment as the explanatory variable. The Kaplan-Meier (K-M) survival curves and survival probability at 2 and 3 years along with the 2-sided 95% CIs will also be provided for each treatment group.

In addition, a stratified Cox regression model will be used to further evaluate the treatment effects on mPFS after adjusting for some prognostic factors. Besides treatment and the stratification factors (Section 5.2), the following prognostic factors will be included in the model simultaneously: age, race (white, non-white), baseline ECOG score, baseline cancer

Brentuximab vedotin (ADCETRIS™)
Statistical Analysis Plan, Study C25003

stage, baseline B symptoms, and PET results from Cycle 2. Additional exploratory analyses may be performed if deemed necessary.

For patients with mPFS events, the reasons leading to the determination of mPFS will be tabulated. For patients without mPFS events, the main reason for censoring will also be tabulated.

The proportional hazard assumptions will be examined and sensitivity analysis may be conducted if appropriate.

5.8.2.1 mPFS Sensitivity Analyses

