5.8.3 Key Secondary Efficacy Endpoint

OS is designated as a key secondary endpoint. The key secondary endpoint will be tested at a 1-sided 0.025 level when the test of mPFS is statistically significant.

OS is defined as the time from the date of randomization to the date of death. Patients without documented death at the time of analysis will be censored at the date last known to be alive.

There will be 2 formal analyses for OS, an OS interim analysis at the time of the final mPFS analysis, and the OS final analysis when 112 deaths have occurred. Overall type I error will be controlled using the O'Brien-Fleming method with a Lan-DeMets alpha spending function.

Brentuximab vedotin (ADCETRIS™)
Statistical Analysis Plan, Study C25003

Stratified log-rank testing will be used to compare OS between the 2 treatment arms. The stratification factors include region and number of IPFP risk factors at baseline (Section 5.2). The hazard ratios along with the 95% CIs (2-sided) will be estimated using a stratified Cox regression model. The Kaplan-Meier method will be used to estimate the distribution of the OS endpoint for each treatment. The 25th, 50th (median), 75th percentiles of survival times (if estimable), and the 2-sided 95% CIs will be presented. Analysis of OS will be performed based on the ITT population.

In addition, a stratified Cox regression model will be used to further evaluate the treatment effects on OS after adjusting for some prognostic factors. Besides treatment and the stratification factors (Section 5.2), the following prognostic factors will be included in the model simultaneously: age, race (white, non-white), baseline ECOG score, baseline cancer stage, baseline B symptoms, and PET results from Cycle 2. Additional exploratory analyses may be performed if deemed necessary.

Subgroup analyses may be performed using subgroups defined for mPFS analyses. Additional analyses of OS may be performed if deemed necessary.

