5.8.4 Other Secondary Efficacy Endpoints

5.8.4.1 Overview of Statistical methods

Other secondary efficacy endpoints mainly consist of 2 types of variables: time to event variables (eg, event-free survival) and binary outcome variables (eg, CR). For time to event variables, the statistical methods will be the same as that for time to death outlined in Section 5.8.3. For binary outcome variables, the statistical methods will be the same as that for CR outlined in Section 5.8.4.2. Other endpoints that don't belong to these 2 categories will be addressed separately.

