5.8.4.8 PET Negativity Rate

PET negativity rate at Cycle 2 is defined as the proportion of patients with negative Cycle 2 PET results. PET negativity is a binary outcome variable.

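### The adjusted models for mPFS, OS and CR condition on the Cycle 2 PET result, which is measured after four randomised doses, so their treatment coefficients are not total treatment effects

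*SAP*

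**What the plan says.** SAP 5.8.2 names the stratified log-rank test as the primary mPFS analysis and takes the hazard ratio from a stratified Cox model containing treatment only. It then adds a second Cox model, adjusted for prognostic factors, to evaluate the treatment effect further. The covariates are age, race, baseline ECOG score, baseline cancer "stage, baseline B symptoms, and PET results from Cycle 2". SAP 5.8.3 repeats the list for OS, again ending with "baseline B symptoms, and PET results from Cycle 2", and SAP 5.8.4.2 repeats it for the CR logistic model.

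The Protocol's Schedule of Events, footnote k, places the scan on Cycle 2 Day 25, ten days "after the 4th dose (after C2D15) of study drug administration". Protocol 4.1 lets a Deauville score of 5 on that scan lead to an optional switch of therapy. Protocol 3.2 lists "The rate of Cycle 2 PET negativity" among the secondary endpoints.

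Three other passages determine how far the models reach:

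- Protocol 8.1.6.2, on CR: "A logistic regression model will be used to estimate the treatment effect in terms of odds ratio".
- SAP 5.8.4.1: "For binary outcome variables, the statistical methods will be the same as that for CR outlined in Section 5.8.4.2". The same section applies the OS methods to the other time-to-event endpoints.
- SAP 5.8.4.8: "PET negativity is a binary outcome variable".

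On missing data, the general default in SAP 5.4.1 is that "missing data will be treated as missing and no data imputation will be applied", unless specified otherwise. Nothing specific is said about missing Cycle 2 scans.

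**The concern.** Cycle 2 PET is a consequence of treatment, and the plan treats it as one by comparing it between arms. Part of any A+AVD benefit may pass through early metabolic response, and conditioning on that response removes this part from the treatment coefficient. What remains is not a clean direct effect either. Unmeasured prognosis may drive both PET and outcome, so conditioning can introduce selection bias, and the scan also influences later therapy. Neither document gives a mediation or direct-effect rationale.

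At stake is how these estimates are read. They are presented as further evaluation of the treatment effect. If A+AVD improves early PET response, they would probably sit closer to 1 than the main estimates and appear to contradict them. Patients without a Cycle 2 scan, possibly including early failures, would probably drop out of a complete-case fit.

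Table 5-4 raises a lesser, related point. It lists three subgroups formed after randomisation (Cycle 2 PET, Cycle 2 Deauville score, receipt of alternative frontline therapy) beside baseline subgroups, without marking them as non-randomised comparisons.

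**Working it through.** **1. Timing.** Dosing is on Days 1 and 15 of each 28-day cycle (Protocol 4.1). By Cycle 2 Day 25 a patient on schedule has had 2 cycles × 2 doses = 4 randomised doses. The covariate is therefore post-randomisation.

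**2. The design figure.** ln(0.81)/ln(0.73) = 0.670, which matches the stated HR. Schoenfeld events for 90% power at 1-sided 0.025: 4 × (1.960 + 1.282)² / (ln 0.67)² = 262.1, so 263 against the stated 260. Power with 260 events is 89.8%. None of this involves PET.

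**3. mPFS with and without PET.** The documents give no Cycle 2 PET rate for ABVD alone. The only A+AVD figure is 14 of 15 negative (93%) in phase 1 (Protocol 1.3).

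- From the plan: 620 per arm, 36-month accrual, 5% annual dropout, 2-year mPFS 81% vs 73%, data cut at the 260th event.
- Assumed: 85% PET-negative on ABVD, PET-positive hazard ratio 2, 3 or 6, and a hazard after 2 years of 10% of the earlier one.
- Method: 1000 simulated trials per scenario, geometric-mean HR.

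The unadjusted HR was 0.66–0.68 in every scenario and significant in 88–92% of runs. The PET-adjusted HR was:

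| PET-negative, A+AVD | PET-adjusted HR (PET HR 2 / 3 / 6) |
|---|---|
| 85% (equal) | 0.66 / 0.66 / 0.63 |
| 88% | 0.68–0.69 across the three |
| 90% | 0.70–0.73 across the three |
| 93% | 0.71 / 0.74 / 0.80 |

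Setting the later hazard at 2% or 30% instead (85% vs 90% negative, PET HR 3) gives 0.70–0.71.

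**4. Varying the ABVD rate.** A separate large-sample Cox calculation fixed A+AVD at 93% negative and 2-year mPFS at 81% vs 73%, with constant hazards within PET group and censoring at 2 years. The unadjusted HR is 0.67 throughout.

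| PET-negative, ABVD | Adjusted HR (PET HR 3 / 5) |
|---|---|
| 93% (equal) | 0.66 / 0.65 |
| 90% | 0.69 / 0.70 |
| 86% | 0.73 / 0.77 |
| 80% | 0.80 / 0.88 |

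Where the PET rates differ, adjustment removes about 9% to 69% of the log hazard ratio.

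**5. CR odds ratio, exact.** Assume CR of 75% vs 81%, so the marginal OR is (0.81/0.19)/(0.75/0.25) = 1.42. Assume also a PET-positive OR for CR of 0.2. For each arm with PET-negative proportion p, solve for a: p·expit(a) + (1 − p)·expit(a + ln 0.2) = CR rate. The adjusted OR is exp(a for A+AVD − a for ABVD).

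- ABVD, p = 0.85: a = 1.4056. Check: 0.85 × 0.8031 + 0.15 × 0.4492 = 0.750.
- A+AVD, p = 0.93: a = 1.6094. Check: 0.93 × 0.8333 + 0.07 × 0.5000 = 0.810.
- Adjusted OR = exp(0.2038) = 1.23.

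The same calculation gives 1.37 at 88%, 1.31 at 90%, and 1.47 with equal PET rates. At 93%, PET-positive ORs from 0.1 to 0.5 give 1.15 to 1.34. With CR of 80% vs 85% and a PET-positive OR of 0.2, the values at 88%, 90% and 93% are 1.36, 1.30 and 1.21.

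**6. PET on PET.** SAP 5.8.4.8 makes PET negativity a binary endpoint. SAP 5.8.4.1 sends binary endpoints to 5.8.4.2, whose logistic model contains Cycle 2 PET. Covariate and outcome are then the same variable. A fit on 1240 simulated patients separated perfectly and gave no usable treatment odds ratio.

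OS was not simulated.

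**The case against.** The strongest reply is that no decision rests on these models. Each comes in addition to a main analysis without PET: log-rank and Cox for mPFS and OS, and stratified CMH for CR with relative risk, odds ratio and absolute difference. This stands, and it limits the severity. The CMH odds ratio in particular means a PET-free CR odds ratio is available. Even so, the SAP's only logistic model, the method the Protocol names for that odds ratio, contains PET, and SAP section 6 records no change from the Protocol.

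Second, the timing is visible, since neighbouring covariates are labelled baseline and PET is not, and the likely attenuation would understate benefit rather than exaggerate it. Both are fair. Visible timing does not make the coefficient a treatment effect, however, and no sentence warns that it is not one.

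Third, the size is assumed and could be nil. That is correct: with equal PET rates there is no attenuation, and 93% rests on 15 patients. Selection bias is a possibility that was not quantified.

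Fourth, the carry-over is partly literal reading. Regressing PET on itself would surface at the first fit, and DFS, DOR and DOCR are confined to responders in any case. The carry-over that matters is to EFS, ORR and CR at the end of frontline therapy. On missing scans, SAP 5.4.1 is only a general default and allows other methods for some outcomes, so exclusion of those patients is an inference.

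**Conclusion.** The concern holds and should be fixed. All three adjusted models include a variable measured after four randomised doses that the plan itself analyses as an outcome, so their treatment coefficients do not estimate total treatment effects. That conclusion needs no assumption about effect size.

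The amount of attenuation does need assumptions. It depends on the PET difference between arms and on how strongly PET predicts outcome. Over the scenarios shown with unequal PET rates, an mPFS HR of about 0.67 becomes 0.68 to 0.88, and a CR odds ratio of about 1.42 becomes 1.15 to 1.37. The PET-negativity model cannot be estimated as written. The primary and key secondary tests, their decision rules, the main hazard ratios, the CMH analysis, type I error and power are untouched.

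**What to change.** In SAP 5.8.2, 5.8.3 and 5.8.4.2, end the covariate list at baseline cancer stage and baseline B symptoms, so that the adjusted models use baseline factors only. Through SAP 5.8.4.1 this also corrects the other secondary endpoints and removes the PET-on-PET model.

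If a PET-adjusted or landmark model is wanted, report it separately as exploratory, say that it does not estimate the total randomised effect, and state how missing Cycle 2 scans are handled.

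In Table 5-4, label the Cycle 2 PET, Cycle 2 Deauville score and alternative-frontline-therapy rows as descriptive, non-randomised comparisons, or move them out of the treatment-effect subgroups.

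The cost is SAP wording only: one phrase deleted in three lists and a label on three table rows. No design figure changes.

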5.8.2.2 Other Analysis

In addition, the primary analysis of mPFS will be performed for the PP population, as well as for the subgroups specified below. The statistical model will be adjusted accordingly to fit the subgroup analyses.

Table 5-4 Subgroups for Subgroup Analysis

Subgroup	Definition of Group
Age	< 60 years; ≥ 60 years
Region	North American, Europe, Asia
Number of IPFP risk factors	0-1; 2-3; 4-7
Baseline cancer stage	stage III; Stage IV
Baseline B symptoms	Present; absent
Cycle 2 PET	Positive; negative
Cycle 2 PET Deauville Score	< 5; 5
Receipt of alternative frontline therapy	Yes; No
Baseline extra nodal sites	0, 1, >1

As HL is a curable disease, a mixture cure survival model will be performed:

$$\text{Survival}_i = P_i + (1 - P_i)S_i$$

where P_i denotes the fraction of patients cured in each arm, S_i is the mPFS survival function for those who are not cured. S_i is assumed to follow Weibull distribution with the same shape parameter for both treatment arms. If Weibull distribution assumption for S_i is not appropriate, other parametric distributions will be considered. Two additional exploratory analyses will also be performed. One for mPFS with definition of frontline therapy restricted to no-switch in therapy. The other for PFS, which is defined as the earlier of (1) documentation of PD or (2) death due to any cause. The statistical methods will be similar to those used for mPFS.

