### **2.2 Secondary Objectives**

The key secondary objective is

- To determine if A+AVD improves OS versus that obtained with ABVD

Other secondary objectives are:

- To determine if A+AVD improves CR rate versus that obtained with ABVD
- To determine the safety profile of A+AVD relative to that of ABVD
- To determine the event-free survival (EFS) obtained with A+AVD and ABVD
- To determine the disease-free survival (DFS) rate obtained with A+AVD and ABVD
- To determine if A+AVD improves overall ORR (defined as CR + PR) versus that obtained with ABVD
- To determine the DOR and duration of complete remission (DOCR) obtained in the A+AVD and ABVD arms
- To determine the rate of patients receiving irradiation for HL not in CR in the A+AVD and ABVD arms
- To determine the rate of patients in CR at the end of frontline therapy in the A+AVD and ABVD arms
- To determine the rate of Cycle 2 PET negativity in patients treated with A+AVD versus those treated with ABVD
- To determine if A+AVD improves health-related quality of life (HRQOL) versus ABVD

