**Brentuximab vedotin (ADCETRIS®)****Clinical Study Protocol C25003 Amendment 7, EudraCT: 2011-005450-60**

performed every 3 months during the first year of posttreatment disease follow-up, then every 6 months until study closure (5 years after the last patient is enrolled). If, for any reason other than death or documented disease progression, a patient discontinues randomization therapy (A+AVD or ABVD) after Cycle 2 Day 25 but before completion of randomization therapy, every effort must be made to obtain PET and CT scans prior to initiation of subsequent therapy for HL. Responses and relapses will be assessed by an IRF. Evaluations will be performed until progressive disease (PD) is documented, receipt of second-line anticancer therapy for HL (including chemotherapy or radiation), death occurs, or the end of study. Patients will be followed for survival until death or for a minimum of 5 years after enrollment of the last patient.

Deauville scoring (see Section 15.6) per IRF will be used to evaluate the results of patients' Cycle 2 Day 25 PET/CT. Patients whose disease earns a Deauville score of 4 or less will continue study drug treatment according to their randomized arm (ABVD or A+AVD). Patients whose PET-positive disease earns a score of 5 may, at the investigator's discretion, receive an alternative regimen (physician's choice) for the remainder of planned frontline therapy. Patients with a Deauville score of 5 who, at investigator's discretion, are taken off study drug will be continue to be followed for response assessment; switching therapy prior to completion of frontline therapy will not be considered an mPFS progression event. Of further note, any switch in therapy prior to completion of frontline therapy will not be considered an mPFS event.

An interim futility analysis will be conducted when the first approximately 348 patients have completed the regimen to which they were randomized (ie, received the planned study drug regimen with no more than 2 missed doses of A+AVD or ABVD) or have discontinued treatment prior to completion. The final analysis of the mPFS primary endpoint will be conducted when 260 mPFS events occur; an interim analysis of OS will also be conducted at that time. The final analysis of OS will be conducted when 112 deaths occur, approximately 4 years after randomization of the last patient.

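### SAP Table 5-4 plans between-arm mPFS comparisons inside three groups formed after randomization (Cycle 2 PET, Cycle 2 Deauville score, alternative frontline therapy), and those hazard ratios need not compare like with like

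*SAP*

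**What the plan says.** SAP 5.8.2 defines the primary analysis as the stratified log-rank test between arms, with a stratified Cox hazard ratio. SAP 5.8.2.2 repeats it in subgroups: "the primary analysis of mPFS will be performed for the PP population, as well as for the subgroups specified below". Six rows of Table 5-4 are baseline variables: age, region, IPFP risk factors, stage, B symptoms and extranodal sites. The other three are Cycle 2 PET (positive or negative), "Cycle 2 PET Deauville Score" (below 5, or 5) and "Receipt of alternative frontline therapy" (yes or no). The table does not separate the two kinds and gives no landmark or caveat. The section says only that the model will be adapted to fit the subgroups.

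For OS, SAP 5.8.3 adds: "Subgroup analyses may be performed using subgroups defined for mPFS analyses". SAP 5.8.4.2 says the same for CR. Both are optional.

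The protocol shows how the three groups arise. The Schedule of Events puts the Cycle 2 scan ten days after the fourth dose. Protocol 2.2 makes its result a between-arm secondary objective: "To determine the rate of Cycle 2 PET negativity in patients treated with A+AVD versus those treated with ABVD". On switching, Protocol 4.1 says: "Patients whose PET-positive disease earns a score of 5 may, at the investigator's discretion, receive an alternative regimen". It adds that a switch before completion of frontline therapy is not an mPFS event.

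Cycle 2 PET is also a covariate in the adjusted Cox models for mPFS (SAP 5.8.2) and OS (5.8.3) and in the logistic model for CR (5.8.4.2).

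**The concern.** Randomization makes the arms comparable as a whole and within any group fixed beforehand. It does not do so within a group that treatment helps to form. Suppose A+AVD turns some patients PET-negative who would have been positive on ABVD. Those patients then count among the negatives in one arm and the positives in the other. The A+AVD positives are left as a harder core, and the A+AVD negatives take in extra patients of intermediate risk. Both shifts work against A+AVD even when the drug helps every type of patient equally.

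The alternative-therapy row adds two problems. The switch is decided by someone who knows the arm; blinded central PET reading protects the score but not the decision. And because a switch is not an mPFS event, what follows partly reflects the substituted regimen.

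At stake is interpretation. Listed beside baseline rows, these results invite statements such as the effect in PET-negative patients, or in patients who did not switch. Randomization does not support such statements.

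**Working it through.** **The plan's own figure.** SAP 5.1 gives 260 events, HR 0.67 and 90% power at 1-sided 0.025. With 1:1 allocation, power = Φ(|ln 0.67| × √260 / 2 − 1.96) = Φ(3.229 − 1.960) = 0.898, which agrees. The 2-year rates agree too: ln 0.81 / ln 0.73 = 0.670. The documents give no figure for the subgroup analyses.

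**Latent-class check.** The documents give no PET-positivity rates for this trial, so they are assumed. The only anchor is the phase 1 study in Protocol 1.3, where 14 of 15 patients in the AVD cohorts were negative, so 1 of 15 (about 7%) was positive.

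Let qA and qB be the positive rates on A+AVD and ABVD. There are three classes of patient:
- positive on either arm, weight qA, assumed hazard 6 times that of the last class;
- positive on ABVD only, weight qB − qA, assumed hazard 3 times;
- negative on either arm, weight 1 − qB, hazard 1.

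Let H be the 2-year cumulative hazard of the last class on ABVD. H is set so that ABVD 2-year mPFS is 73% overall. Each class on A+AVD has survival S^0.67, so the true HR is 0.67 in every class. The within-row HR is taken as ln S(A+AVD) / ln S(ABVD) at 2 years.

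For 7% versus 10%:
- H = 0.2508. ABVD class survival is exp(−6H) = 0.222, exp(−3H) = 0.471 and exp(−H) = 0.778. Check: 0.07 × 0.222 + 0.03 × 0.471 + 0.90 × 0.778 = 0.730.
- A+AVD class survival, each raised to the power 0.67, is 0.365, 0.604 and 0.845.
- PET-positive: A+AVD 0.365; ABVD (0.07 × 0.222 + 0.03 × 0.471) / 0.10 = 0.297. HR = ln 0.365 / ln 0.297 = 0.83.
- PET-negative: A+AVD (0.03 × 0.604 + 0.90 × 0.845) / 0.93 = 0.838; ABVD 0.778. HR = ln 0.838 / ln 0.778 = 0.71.

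Other inputs, same formulas:

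| Positive, A+AVD / ABVD | Hazard multiples | HR in positives | HR in negatives |
|---|---|---|---|
| 7% / 7% | 6, 3, 1 | 0.67 | 0.67 |
| 7% / 10% | 6, 3, 1 | 0.83 | 0.71 |
| 7% / 15% | 6, 3, 1 | 0.97 | 0.77 |
| 5% / 15% | 6, 3, 1 | 1.06 | 0.79 |
| 5% / 15% | 8, 2, 1 | 1.67 | 0.74 |
| 3% / 15% | 10, 1.5, 1 | 3.00 | 0.71 |

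The overall 2-year ratio is 0.69 in all of these. The first line shows no distortion when the arms do not differ in positivity.

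**Simulated switching.** This used 620 patients per arm and 150 replicates per scenario. The chance of switching depended on arm and on an unmeasured risk factor, and the HR was 0.67 given that factor. With 5% versus 15% switching and moderate selection, the median HR was 0.90 in switchers and 0.81 in non-switchers, against 0.72 overall. With strong selection it was 1.22 and 0.92, against 0.75. Across all scenarios the non-switcher median ran from 0.70 to 0.99. With equal switching (7% each) it was 0.78 and 0.70, against 0.72; these departures from 0.67 come from omitting the risk factor in the Cox model, not from different selection by arm. The simulation has no plateau and no dropout and yields 406 to 425 events rather than 260, so it shows direction, not size.

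**The case against.** The strongest reply is that nothing depends on these rows. They stand under a heading for other analyses, and SAP 3.2 attaches decisions only to ITT mPFS and then OS. No alpha, claim or stopping rule uses a subgroup. That stands, and it limits the weight of the point.

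A reader might go further and infer that A+AVD would look worse in both PET rows while being better overall. Such an example can be built. Suppose 85% of patients are always negative (event risk 20%), 8% always positive (75%), and 7% positive only on ABVD (60% on ABVD, 30% on A+AVD). Overall risk is 0.170 + 0.021 + 0.060 = 25.1% on A+AVD and 0.170 + 0.042 + 0.060 = 27.2% on ABVD. The negatives show 0.191 / 0.92 = 20.8% versus 20.0%, and the positives 75% versus 0.102 / 0.15 = 68%. But this assumes no effect in 93% of patients (85% + 8%). The plan assumes event risks of 19% versus 27% and an HR of 0.67. With that HR in every class, reversal appeared only among PET-positive or switched patients. Medians in the other group stayed below 1, although under the strongest simulated selection 45% of single trials gave a non-switcher HR above 1.

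Nor do the documents show that these rows will be presented as a headline result, or that OS and CR subgroups will be run; for those the SAP says only that they may be.

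The need to remain on study until classified is a small matter for PET, since the scan falls at about Day 53 (28 + 25). For the alternative-therapy row, a patient who dies early simply counts as not switched.

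Labelling the rows exploratory and non-causal would be a lighter remedy. It would reduce misreading but leave the uninterpretable hazard ratio in the report.

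**Conclusion.** The point holds as a matter of interpretation in supportive analyses. The SAP commits to between-arm mPFS comparisons in three groups formed after treatment has begun, one of which is itself compared between arms as an endpoint. The hazard ratios are distorted whenever treatment changes PET status or switching differs by arm.

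The size depends on assumed positivity rates and risk gradients. At 7% versus 10%, the HR in PET-positives is about 0.83 against a true 0.67. At 5% versus 15%, it is 1.06 to 1.67 under the two gradients tried. In PET-negatives the result is attenuated but stays below 1 (0.71 to 0.79 where positivity differs, in the cases tabulated). Where positivity and selection are equal, there is no bias. Reversal is therefore possible but not shown to be likely. The ITT primary test and its type I error are untouched. The change is worth making because it is cheap, not because the trial's conclusion is at risk.

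**What to change.** - Remove Cycle 2 PET, Cycle 2 Deauville score and receipt of alternative frontline therapy from Table 5-4 as between-arm comparisons. State that the optional OS and CR subgroup analyses use the baseline rows only.
- Report outcomes by Cycle 2 PET and Deauville score descriptively within each arm, from a landmark at the Cycle 2 scan.
- Report switching descriptively within each arm: counts, timing, and outcomes measured from the switch. Do not use the Cycle 2 landmark here. Switching follows that scan, so grouping by it at the scan would use future information. Give no between-arm hazard ratio or p-value.
- For the same reason, drop Cycle 2 PET from the covariates in the adjusted mPFS, OS and CR models (SAP 5.8.2, 5.8.3, 5.8.4.2). Adjusting a whole-trial estimate for a result of treatment raises the same problem.

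This is an edit to one SAP table and three model statements, with no new data. The downside is small: there will be no between-arm hazard ratio by PET or switch status, which clinical readers may want.
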